5.1.3 Management of Patients Who Experience Adverse Events

5.1.3.1 Dose Modifications

No dose modifications are permitted in this study, whether by varying the amount of study drug volume injected or the frequency of procedure per protocol (i.e., all participants will receive 20 mL of study drug per injection on a *Q8W* basis).

5.1.3.2 Treatment Interruption

Study drug may be temporarily suspended in patients who experience toxicity considered to be related to study drug. If study drug has been withheld for >60 days because of signs of persistent drug-induced toxicity or if the scheduled dose has been missed, the investigator should consult the Medical Monitor to determine if discontinuation from study drug is warranted. Study drug may be suspended for reasons other than toxicity (e.g., surgical procedures) with Medical Monitor approval. The investigator and the Medical Monitor will determine the acceptable length of treatment interruption.

5.1.3.3 Management Guidelines

Guidelines for management of specific adverse events are outlined in [Table 3](#). Additional guidelines are provided in the subsections below.

Initial clinical laboratory tests with results meeting criteria for withholding study drug must be repeated on new specimens as soon as possible, and results must be available prior to administering the next dose of study drug. In general, patients who do not reach the stopping rule may continue dosing; however, the investigator and Sponsor should confer as to whether additional close monitoring of the patient is indicated.

Table 3 Guidelines for Management of Patients Who Experience Adverse Events

Event	Action to Be Taken
Elevations in CSF WBC count or proteins or suspected meningitis, radiculitis, arachnoiditis, or other acute neurologic symptoms	
 Withhold study drug if diagnosis of meningitis, radiculitis, arachnoiditis, or acute neurologic symptoms is suspected and initiate appropriate diagnostic work-up as indicated. Clinical signs and symptoms (e.g., headache, stiff neck, fever) plus confirmatory WBC count are required for diagnosis of suspected meningitis, and clinical signs and symptoms are required for diagnosis of radiculitis, arachnoiditis, or acute neurologic symptoms. Isolated low-level (e.g., 5–50 WBC count) elevations in CSF WBC count without clinical symptoms does not meet criteria for diagnosis of suspected meningitis. The Medical Monitor should be consulted in all cases where WBC count CSF elevations above 10 are present, or a change from baseline in CSF proteins greater than twice baseline or where there is uncertainty to discuss next steps of patient management in the study. If diagnosis of suspected meningitis, radiculitis, arachnoiditis, or other acute neurologic symptoms is refuted, the study drug may be resumed after consultation with the Medical Monitor. In the event meningitis, radiculitis, arachnoiditis, or acute neurologic symptom diagnosis is confirmed, standard-of-care therapies should be instituted as indicated.
Thrombocytopenia	
 If platelet count is $\leq 100,000/\text{mm}^3$: 
 Monitor platelet count weekly If platelet count is $\leq 75,000/\text{mm}^3$ and $> 50,000/\text{mm}^3$ in the absence of major bleeding or clinically relevant non-major bleeding: 
 Withhold study drug until the platelet count has recovered to $> 100,000/\text{mm}^3$. The suitability of the patient for continued dosing and frequency of monitoring should be discussed with the Medical Monitor. If platelet count is $\leq 50,000/\text{mm}^3$: 
 Permanently discontinue study drug. Monitor platelet counts daily until two successive values show improvement. Then monitor every 2–3 days until platelet count is stable, and at least weekly until platelet count returns to normal. Treatment per standard of care should be considered for patients whose platelet count is $< 25,000/\text{mm}^3$.

Table 3 Guidelines for Management of Patients Who Experience Adverse Events (cont.)

Decreased renal function	
 Withhold study drug in the event of a persistent (>2 weeks) decrease in eGFR or CrCl or increase in creatinine, as defined below: 
 eGFR (using Cockcroft-Gault) or CrCl < 60 mL/min Creatinine level increase of 2.0 \times above baseline Study drug may be resumed when follow-up test results show that the patient no longer meets the dose interruption criteria.
Elevated liver enzymes	
 ALT or AST is $>3 \times$ ULN: 
 Monitor weekly until ALT and AST return to $\leq 1.2 \times$ ULN. Further investigation into the liver enzyme elevations may include hepatitis serologies and other diagnostic tests at the discretion of the investigator in consultation with the Medical Monitor. Withhold study drug in the event of liver enzymes that meet the following criteria without an alternative explanation (as discussed with the Medical Monitor): 
 ALT or AST $>5 \times$ ULN ALT or AST $>3 \times$ ULN, combined with total bilirubin $>2 \times$ ULN or INR >1.5 ALT or AST $>3 \times$ ULN coinciding with new appearance of fatigue, nausea, vomiting, right upper quadrant pain or tenderness, fever, rash, and/or concomitant eosinophilia. Discontinue study drug permanently if levels do not return to baseline after 30 days.

CrCl=creatinine clearance; CSF=cerebrospinal fluid; eGFR=estimated glomerular filtration rate; ULN=upper limit of normal.

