4.5 STUDY ASSESSMENTS

The schedule of activities to be performed during the study is provided in [Appendix 1](#). All activities should be performed and documented for each patient.

Patients will be closely monitored for safety and tolerability throughout the study. Patients should be assessed for toxicity prior to each dose; dosing will occur only if the clinical assessment and local laboratory test values are acceptable.

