4.5.5 Collection of Cerebrospinal Fluid (Lumbar Puncture Procedure)

Within 72 hours prior to performing each scheduled lumbar puncture, local laboratory analysis of coagulation factors (INR *and/or* PT, aPTT) and platelets must be conducted and the results reviewed. The lumbar puncture should be performed at approximately the same time at each visit (ideally in the morning between 8:00 a.m. and 12:00 noon or in the early afternoon between 12:00 noon and 3:00 p.m.) to minimize potential diurnal variation of CSF parameters. CSF fluid (20 mL) is to be collected for analyses using a lumbar puncture collection kit. If there are difficulties in collecting 20 mL of CSF fluid, a minimum of 5 mL should be collected over a maximum of 60 minutes, *once CSF flow has been established*. The operator must confirm CSF flow is present prior to injecting drug. A 24G atraumatic needle, *as specified in the LP procedure and CSF collection guidelines manual*, should be used to minimize risk of post-lumbar puncture syndrome. Depending on institutional guidelines, local anesthesia should be used for the procedure. Sedation may not be used. Spinal ultrasound may be used for the lumbar puncture procedure if deemed necessary, but ultrasound is not required. Ultrasound guidance may be used if attempts at lumbar puncture without imaging are unsuccessful, if it is local practice to use ultrasound, or if institutional guidelines dictate use of ultrasound with each lumbar puncture. For details on the lumbar puncture and IT bolus dosing procedure, please refer to the *LP procedure and CSF collection guidelines manual* and instructional video.

Administration will occur via a lumbar puncture using a needle inserted into the L3/L4 space, although placement at a different level (either in the space above or the space below) is allowed if patient anatomy or clinical judgment dictates. *The left lateral position is mandatory in the first instance for the procedure, unless patient-specific factors require use of the upright, sitting position. Whichever position is used, once access is established to the IT space, the entire IT bolus procedure should be completed*

in the same position, to limit the risk of the needle losing position while the spinal needle is inserted.

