4.6.1 Study Treatment Discontinuation

Patients must permanently discontinue study treatment if they experience any of the following:

- Any medical condition that the investigator or Sponsor determines may jeopardize the patient's safety if he or she continues to receive study treatment
- Investigator or Sponsor determination that treatment discontinuation is in the best interest of the patient
- Pregnancy
- *Loss of capacity to consent, if legal guardian consent is not possible*

The primary reason for study treatment discontinuation should be documented on the appropriate eCRF. Patients who discontinue study treatment prematurely will not be replaced.

All patients who discontinue study treatment prematurely but do not withdraw consent for continued participation in the study will return to the clinic for study visits at Weeks 53 and 69 (if not already completed) for collection of at least the data for the primary and secondary endpoints (see Sections 2.1.1, 2.1.2, and 2.2). If the early treatment termination visit falls within ± 30 days of either scheduled visits at Week 53 or Week 69, then only early treatment termination will be considered. Patients will also attend the scheduled end-of-treatment visit at Week 101 *window*.

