There are specific contraindications to performing lumbar puncture. These include unstable cardiorespiratory status, where positioning patient for lumbar puncture may not be tolerated, signs of cerebral herniation or incipient cerebral herniation, signs of increased intracranial pressure, or focal neurological findings on examination. In those patients, lumbar puncture (and IT treatment administration) should not be performed and appropriate diagnostic work-up should be initiated. On a case-by-case basis and following discussion with the Medical Monitor, such patients may be able to resume treatment. Previous lumbar surgery is an exclusion criterion for this study.

In the setting of HD, for the purposes of lumbar puncture and IT bolus injection of RO7234292, moderate to severe truncal chorea may also be prohibitive.

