5.1.2.3 Thrombocytopenia

Reductions in platelet count have been observed after systemic administration of some 2'-MOE chimeric ASOs to clinical trial subjects. However, no clinically significant reductions in platelet counts *have been observed in clinical studies for RO7234292 to date*. In one 13-week and one 9-month IT toxicity studies of RO7234292 in the cynomolgus monkey, there were no effects on hematology or coagulation parameters.

No clinically significant reduction in platelet counts was observed in the completed RO7234292 Phase I/IIa study. In the ongoing phase II OLE study (BN40697), no events of thrombocytopenia have been reported to date (9-month data).

Platelet counts will be monitored at each study visit prior to lumbar puncture. See [Table 3](#) for patient stopping and *treatment* discontinuation rules.

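### Table 3 requires study drug to be withheld at platelets >50,000 to ≤75,000/mm³ only when the patient is not bleeding; the same count with bleeding has no stated dosing action

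*Protocol*

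**What the plan says.** Section 5.1.2.3 states: "Platelet counts will be monitored at each study visit prior to lumbar puncture". It then refers sites to Table 3 for the stopping and discontinuation rules and gives no rule of its own.

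The thrombocytopenia row of Table 3 (Section 5.1.3.3) has three tiers that bear on dosing:

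- **≤100,000/mm³:** weekly platelet counts.
- **≤75,000 and >50,000/mm³, "in the absence of major bleeding or clinically relevant non-major bleeding":** withhold until recovery above 100,000/mm³, and discuss continued dosing and monitoring frequency with the Medical Monitor.
- **≤50,000/mm³:** permanent discontinuation, with no condition on bleeding.

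The text before the table adds two general rules. Results that meet a withholding criterion must be repeated on a new specimen before the next dose. Patients who have not reached a stopping rule, in general, "may continue dosing; however, the investigator and Sponsor should confer as to whether additional close monitoring of the patient is indicated".

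**The concern.** The bleeding qualifier points the wrong way. Bleeding at a given platelet count makes a lumbar puncture more dangerous, yet in the middle band it takes the patient out of the mandatory hold. Read literally, a patient at 60,000/mm³ without bleeding must not be dosed, while a patient at 60,000/mm³ with major bleeding has no platelet-specific dosing instruction.

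This matters in this trial because all study drug is given intrathecally by lumbar puncture. Section 5.1.1.2 describes spinal hematoma as very rare but important and names susceptibility to bleeding as a risk factor for it. The entry criteria in Section 4.1.2 treat bleeding as aggravating: counts of 125,000 to 150,000/mm³ are allowed only when there is no current bleeding diathesis or coagulopathy. Table 3 reverses that logic at a much lower count.

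**Working it through.** The question is whether the rule covers every case, so the check sets each platelet band against bleeding status. Here bleeding means major or clinically relevant non-major bleeding, the terms of the qualifier; trivial bleeding still falls under the withhold line.

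| Platelets (/mm³) | Without such bleeding | With such bleeding |
|---|---|---|
| >75,000 to ≤100,000 | Weekly monitoring | Weekly monitoring |
| >50,000 to ≤75,000 | **Withhold until >100,000; Medical Monitor discussion** | **Weekly monitoring only** |
| ≤50,000 | Permanent discontinuation | Permanent discontinuation |

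Five of the six cells are consistent: the action with bleeding is never weaker than without. The exception is the middle band with bleeding.

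Falling outside the withhold line has further consequences for that patient:

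1. The recovery threshold of >100,000/mm³ does not apply.
2. The Medical Monitor discussion, which is attached to that line, is not called for.
3. The repeat-specimen rule is not triggered, because it covers only results that meet a withholding criterion.
4. The default for patients who have not reached a stopping rule applies: dosing may in general continue, and the investigator and Sponsor confer about closer monitoring rather than about holding the dose.

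The rest of the protocol was then searched for a rule that fills the cell:

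- **Section 4.5:** "dosing will occur only if the clinical assessment and local laboratory test values are acceptable". This is mandatory, but acceptable is not defined.
- **Section 4.5.5:** local coagulation tests and "platelets must be conducted and the results reviewed" within 72 hours before each puncture. No count is given below which the puncture is cancelled.
- **Section 4.6.1:** permanent discontinuation is mandatory for "Any medical condition that the investigator or Sponsor determines may jeopardize" the patient's safety. It takes effect only once that judgement has been made.
- **Section 5.1.3.2:** "Study drug may be temporarily suspended in patients who experience toxicity considered to be related to study drug". This is permissive and limited to toxicity attributed to the drug.
- **Section 5.1.1:** "There are specific contraindications to performing lumbar puncture". Those listed cover cardiorespiratory instability, cerebral herniation, raised intracranial pressure and focal neurological findings. Neither low platelets nor active bleeding is named.
- **Section 4.1.2:** the platelet and bleeding criteria govern entry only.
- **Appendix 5:** grades the severity of platelet decreases and gives no dosing action.

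None of these gives a platelet or bleeding threshold for the empty cell.

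**Number of occasions.** Table 1 gives 2 loading plus 11 maintenance administrations: 2 + 11 = 13 dosing punctures in each arm (in the Q16W arm, 2 + 5 active + 6 placebo = 13). One CSF-sampling puncture at Week 101 makes 13 + 1 = 14 for a completer. The pre-puncture platelet check applies to all 14; the dose-withholding rule itself applies to 13.

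**The case against.** The best case on the other side is that the gap is real but has little practical effect.

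The pre-dose requirement in Section 4.5 is mandatory, and a bleeding patient at or below 75,000/mm³ would have to pass both its clinical and its laboratory limb. The default that dosing may continue is hedged as general and does not override that requirement. The list of lumbar puncture contraindications is introduced as a set of inclusions, so its silence on platelets does not make puncture acceptable, and Section 5.1.1 also asks for careful assessment of the patient. Major bleeding would ordinarily be a serious adverse event, reported to the Sponsor within 24 hours (Sections 5.2.2 and 5.4). A site would more naturally read the qualifier as implying that bleeding calls for something stricter. The population is also selected: bleeding diathesis and coagulopathy are exclusions, and antiplatelet and anticoagulant drugs other than low-dose aspirin are prohibited.

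Most of this stands as mitigation. A competent investigator would very probably hold the dose, and the coincidence of such a count with such bleeding should be rare. It does not supply the missing rule. Each safeguard depends on someone's judgement, reporting a serious adverse event does not itself stop a dose, and clinically relevant non-major bleeding may not be serious. If a stricter action was intended for bleeding patients, the protocol does not state it.

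**Conclusion.** The point holds. In the band >50,000 to ≤75,000/mm³, the explicit stopping rule is weaker for the patient who is bleeding than for the one who is not, and no other text gives a threshold for that case. The lower-risk case has a fixed rule; the higher-risk case is left to site and Sponsor judgement.

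The expected frequency is low. Section 5.1.2.3 reports no clinically significant platelet reductions with this drug and no thrombocytopenia events in the 9-month extension data. The six-cell table shows that the gap exists, and the count of 14 punctures shows how often the check recurs; neither estimates a probability of harm. The patient is not unprotected, and efficacy, sample size and analysis are unaffected. The defect should be corrected because it sits in an operative safety rule, concerns the higher-risk patient and is trivial to repair.

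The conclusion rests on a literal reading of Table 3. The protocol does not show which action was intended for the bleeding patient.

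**What to change.** Add one line to the thrombocytopenia row of Table 3: at ≤75,000 and >50,000/mm³ with major or clinically relevant non-major bleeding, at least withhold study drug and lumbar puncture, with permanent discontinuation if the sponsor's medical team so decides.

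Deleting the bleeding qualifier would also close the gap, because withholding would then apply across the whole band. It is the weaker option: it would give the bleeding patient the same temporary hold, resumable after recovery above 100,000/mm³, and so might settle on a milder action than was intended.

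Either change costs one line or one clause in Table 3, with no effect on visits, sample size or analysis.

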5.2 SAFETY PARAMETERS AND DEFINITIONS

Safety assessments will consist of monitoring and recording adverse events, including serious adverse events and adverse events of special interest, performing protocol-specified safety laboratory assessments, measuring protocol-specified vital signs, and conducting other protocol-specified tests that are deemed critical to the safety evaluation of the study.

Certain types of events require immediate reporting to the Sponsor, as outlined in Section 5.4.

5.2.1 Adverse Events

According to the ICH guideline for Good Clinical Practice, an adverse event is any untoward medical occurrence in a clinical investigation subject administered a pharmaceutical product, regardless of causal attribution. An adverse event can therefore be any of the following:

- Any unfavorable and unintended sign (including an abnormal laboratory finding), symptom, or disease temporally associated with the use of a medicinal product, whether or not considered related to the medicinal product
- Any new disease or exacerbation of an existing disease (a worsening in the character, frequency, or severity of a known condition) (see Sections [5.3.5.9](#) and [5.3.5.10](#) for more information)
- Recurrence of an intermittent medical condition (e.g., headache) not present at baseline
- Any deterioration in a laboratory value or other clinical test (e.g., ECG, X-ray) that is associated with symptoms or leads to a change in study treatment or concomitant treatment or discontinuation from study drug
- Adverse events that are related to a protocol-mandated intervention, including those that occur prior to assignment of study treatment (e.g., screening invasive procedures such as biopsies)

5.2.2 Serious Adverse Events (Immediately Reportable to the Sponsor)

A serious adverse event is any adverse event that meets any of the following criteria:

- Is fatal (i.e., the adverse event actually causes or leads to death)
- Is life threatening (i.e., the adverse event, in the view of the investigator, places the patient at immediate risk of death)

This does not include any adverse event that, had it occurred in a more severe form or was allowed to continue, might have caused death.

- Requires or prolongs inpatient hospitalization (see Section [5.3.5.11](#))
- Results in persistent or significant disability/incapacity (i.e., the adverse event results in substantial disruption of the patient's ability to conduct normal life functions)
- Is a congenital anomaly/birth defect in a neonate/infant born to a mother exposed to study drug
- Is a significant medical event in the investigator's judgment (e.g., may jeopardize the patient or may require medical/surgical intervention to prevent one of the outcomes listed above)

The terms "severe" and "serious" are not synonymous. Severity refers to the intensity of an adverse event (e.g., rated as mild, moderate, or severe, or according to National Cancer Institute Common Terminology Criteria for Adverse Events [NCI CTCAE]; see

Section 5.3.3); the event itself may be of relatively minor medical significance (such as severe headache without any further findings).

Severity and seriousness need to be independently assessed for each adverse event recorded on the eCRF.

Serious adverse events are required to be reported by the investigator to the Sponsor immediately (i.e., no more than 24 hours after learning of the event; see Section 5.4.2 for reporting instructions).

5.2.3 Adverse Events of Special Interest (Immediately Reportable to the Sponsor)

Adverse events of special interest are required to be reported by the investigator to the Sponsor immediately (i.e., no more than 24 hours after learning of the event; see Section 5.4.2 for reporting instructions). Adverse events of special interest for this study are as follows:

- Cases of potential drug-induced liver injury that include an elevated ALT or AST in combination with either an elevated bilirubin or clinical jaundice, as defined by Hy's Law (see Section 5.3.5.7)
- Suspected transmission of an infectious agent by the study drug, as defined below:
Any organism, virus, or infectious particle (e.g., prion protein transmitting transmissible spongiform encephalopathy), pathogenic or non-pathogenic, is considered an infectious agent. A transmission of an infectious agent may be suspected from clinical symptoms or laboratory findings that indicate an infection in a patient exposed to a medicinal product. This term applies only when a contamination of the study drug is suspected.

5.3 METHODS AND TIMING FOR CAPTURING AND ASSESSING SAFETY PARAMETERS

The investigator is responsible for ensuring that all adverse events (see Section 5.2.1 for definition) are recorded on the Adverse Event eCRF and reported to the Sponsor in accordance with instructions provided in this section and in Sections 5.4–5.6.

For each adverse event recorded on the Adverse Event eCRF, the investigator will make an assessment of seriousness (see Section 5.2.2 for seriousness criteria), severity (see Section 5.3.3), and causality (see Section 5.3.4).

